12. The EuroQol – 5D (EQ-5D), Functional Assessment of Cancer Therapy – Bone Marrow Transplant (FACT-BMT), and Work Productivity and Activity Impairment Questionnaire (WPAI) are to be completed by the subject prior to any other study assessments or visit procedures. Subjects are to complete these assessments in the following order: EQ-5D first, FACT-BMT second, WPAI:GH last. For all 3 patient-reported outcome measures, i.e. EQ-5D, FACT-BMT, WPAI, the answers must come from the subject. If the subject is unable to fill out the questionnaire, the assessment should not be performed. If the subject is unable to answer a question, the rest of the questionnaire still needs to be completed.
13. Immunogenicity laboratories include collection of blood for the glycoprotein B (gB) antibody and phosphoprotein 65 (pp65) T-cell assays. Samples are to be drawn on visits V2, V5, V8, V9, V11 and V14. Samples for T-cell assays will not be collected if the absolute lymphocyte count is known to be $< 500 \text{ mm}^3$ by local or central laboratory measurement. If the visit coincides with a study drug administration, the sample will be drawn prior to injection.
14. The platelet count must be at least $\geq 50000 \text{ mm}^3$ (spontaneously or after platelet transfusion) performed by the local laboratory within 3 days prior to all study drug injections. Prior to all study drug injections, confirmation must be made that there is no medical contraindication to an IM injection. Results received in an equivalent local unit of measure must be converted to SI units. If the subject's platelet count does not meet this threshold at the time of the visit, the subject may return for the study drug injection and local reactogenicity assessment at a later time within the allowable window for the visit. If the subject's platelet count does not meet this threshold during the visit window, the dose must be skipped and the corresponding follow-up safety laboratory and reactogenicity assessment should not be done. The second injection should be given as close to, but not prior to, day 14 as possible.
15. Subjects who consent to participate in the pharmacogenomics (PGx) substudy will have a saliva sample collected during the baseline visit (V2), after randomization but prior to the first dose of study drug.

Footnotes continued on next page

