24. If the subject does not meet the criteria for dosing by day 40, V5 procedures (except study drug injection and local reactogenicity assessment) need to be completed within 5 days of day 40 (day 40 to 45) and V6 should be skipped.
25. The day 365 visit must occur on day 365 +14 days (between day 365 to 379); it cannot occur prior to day 365 for subjects who do not prematurely withdraw from both treatment and continued follow-up. For a subject who prematurely withdraws from the study (discontinues treatment with no continued follow-up), the study completion visit is to be completed within 14 days of study withdrawal.

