5.7 Immunogenicity Analysis Set

The Immunogenicity Analysis Set (IAS) will include subjects who received at least 1 dose of randomized study drug and for whom at least 1 post-transplant immunogenicity measurement is available.

The IAS will be used for analyses of the immunogenicity data.

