6.1.4 Immunogenicity Variables

An indicator of immunogenicity elicited by the vaccine is expected to be an increase in Gb-specific antibody levels and the T-cell response to the pp65 protein over time compared with the placebo group.

Two immunogenicity assessments will be performed:

1. T-cell response to viral protein pp65 using cultured ELISpot .
2. Antibody response to gB antigen using an ELISA-based platform.

Assessments will be done from peripheral blood mononuclear cells (T-cells) or serum samples (antibody) isolated over the course of the trial. Time points of the assessments are as follows:

On Visits V2, V5, V8, V9 and V11 and V14:

- Samples for T-cell assays will not be collected if the Absolute Lymphocyte Count (ALC) is known to be $\leq 500 \text{ mm}^3$ by local or central laboratory measurement.
- If the visit coincides with a study drug administration, the sample will be drawn prior to injection.

Further details will be available in the Laboratory Manual.

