7.4.2.1 Key Secondary Endpoint - Protocol-Defined CMV Viremia

The protocol-defined CMV viremia through 1 year post-transplant is defined as a CMV plasma viral load ≥ 1000 IU/mL by the central laboratory. The plasma viral load after transplantation through day 380 from transplantation day will be considered. A subject who has more than one time with CMV viral load ≥ 1000 IU/mL will be counted once. This endpoint will be analyzed by 2 statistical methods for FAS, mFAS and PPS-FAS.

A Cox proportional subdistributional hazards model will be used for the time-to-first protocol-defined CMV viremia through 1 year post-transplant. This model accounts for the competing risk of death, after which CMV Viremia can no longer be observed. A subject who has more than 1 incidence of having CMV viral load ≥ 1000 IU/mL will consider the first time of having this event. The Cox model will include treatment group, donor-recipient relatedness, donor CMV serostatus as factors in the model. From this model, 1 – Hazard Ratio and its 95% CI will be calculated. The p-value from this model will be calculated.

The treatment effect will also be evaluated with the following null hypothesis:

$$H_0: 1\text{-Hazard Ratio} \leq 20\%.$$

While the alternative hypothesis is:

$$H_1: 1\text{-Hazard Ratio} > 20\%.$$

The p-value for the above hypothesis tests will use a Wald statistic using the Cox model parameter estimate for the treatment effect, θ_t :

$$Z = (\theta_t - \ln(1-20\%))/S.E.(\theta_t)$$

CIFs will be used to estimate the crude incidence of CMV Viremia by treatment group while accounting for the competing risk of death.

The analysis window extends to day 380 from the transplantation day in order to accommodate the protocol allowed visit windows. If a subject's first event is after day 380, this subject will be censored on day 380 as the 1-year post transplantation is the primary

study period. A subject without an event will be censored on the last day of central laboratory assessment. In other words, if a subject has a central laboratory assessment beyond day 380 that is negative, this subject will be censored on day 380. A subject who dies prior to reporting CMV Viremia will be handled using a competing risks model.

Additionally, the same CMH method as in the primary endpoint will be used to calculate odds ratio and its 95% CI and 1-relative risk and its 95% CI. The p-value from this method will also be calculated.

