7.4.3.2 Duration of Hospitalization, Health Economic, and Quality of Life Variables

Duration of hospitalizations, and days in emergency room, in days per year will be compared between treatments using descriptive statistics.

The number of emergency room visits, and Non-protocol-related physician visits, also will be compared between treatments using descriptive statistics.

The EQ-5D dimensions will be summarized as categorical variables by treatment arm at each visit and at final visit. Change from baseline in the EQ-5D VAS score will be summarized by treatment arm at each visit and at Final visit.

Total FACT-BMT and the corresponding changes from baseline will be summarized by treatment arm at each visit and at Final Visit.

The percent activity impairment due to health from the WPAI: GH and corresponding changes from baseline will be summarized by treatment arm at each visit and at Final Visit.

Treatments will be compared with respect to each of these scales using analysis of covariance (ANCOVA) of change from baseline to final visit with treatment, donor-recipient relatedness, and donor CMV serostatus as factors and baseline value as a covariate.

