7.4.3.3 Immunogenicity Variables

T-cell responses to pp65 and gB-specific antibody levels will be summarized by visit and treatment group on the original scale. A plot of each of the immune responses over time by treatment will be produced. The comparisons between treatments will be made at each measurement visit using Wilcoxon rank sum test without adjusting for the multiplicity on the original scale. In addition, each of the immune response variables post baseline on the 10 based log scale will be analyzed using repeated measures model, where the randomization stratum, treatment, time, and treatment by time interaction will be the explanatory variables. The self-consistent sandwich correlation structure will be used. If the test for the time by treatment interaction is significant (p value <0.1) the overall treatment group comparison will not be displayed in the plots.

As an exploratory analysis, the relationship between immunogenicity variables and treatment outcome will be assessed using logistic regression method. The treatment outcome is if subject is free of CMV viremia through one year post-transplant. The optimal cutoff values of the respective immunogenicity variables that will define the treatment outcome will be explored in terms of maximizing the area under the receiver operating characteristic (ROC) curves.

All analyses of immunogenicity variables will be based on the IAS.

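### SAP 7.4.3.3 (exploratory): the repeated measures model leaves out the pre-dose V2 value, and the viremia correlate analysis names no visit and does not require the sample to precede viremia

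*SAP*

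**What the plan says.** **Repeated measures model.** SAP 7.4.3.3 states that "each of the immune response variables post baseline on the 10 based log scale will be analyzed using repeated measures model". The explanatory terms are randomization stratum, treatment, time and their treatment-by-time interaction. V2 is summarized and plotted and has its own Wilcoxon comparison, but it is not a term in the model. "Samples are to be drawn on visits V2, V5, V8, V9, V11 and V14" (SAP Table 1, footnote 13), and at dosing visits the draw precedes the injection, so V2 is a true baseline. SAP 7.4.3.2 does adjust the quality-of-life scales for baseline, "with treatment, donor-recipient relatedness, and donor CMV serostatus as factors and baseline value as a covariate".

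**Correlate analysis.** The same section relates immunogenicity variables to outcome by logistic regression and looks for ROC cutoffs. "The treatment outcome is if subject is free of CMV viremia through one year post-transplant". It gives no visit, no rule on sample order and no rule for a subject who dies before viremia. For time to viremia, SAP 7.4.2.1 does handle death: "This model accounts for the competing risk of death, after which CMV Viremia can no longer be observed".

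**Who has samples.** The analysis set takes subjects "for whom at least 1 post-transplant immunogenicity measurement is available" (SAP 5.7). "Samples for T-cell assays will not be collected if the Absolute Lymphocyte Count (ALC) is known to be" at or below a stated limit (SAP 6.1.4).

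**Timing.** Protocol 2.2.2 expects first viremic episodes about 30 days after transplant. V5 is aimed at day 14 but may fall up to day 40. If dose 2 is not given, V5 procedures "need to be completed within 5 days of day 40 (day 40 to 45"). V8 is 10 to 14 days after a dose at day 60 ± 5, so day 65 to 79. V9 and V11 are at days 90 and 180 (each ± 10), and V14 is at day 365 to 379.

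**The concern.** The model-based treatment comparison of gB antibody and pp65 T-cell response is less precise than the collected data allow.

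The timing gap is the weightier of the two. A sample taken after viremia cannot predict it, and its value may reflect the infection or its treatment. The sign is open: CMV antigen may raise the response, while Protocol 1.1 notes that CMV-specific antiviral therapy (AVT) is myelosuppressive. If such samples enter, the regression or its cutoff may show an association where none exists, or may hide or reverse a real one. A published cutoff could then be read as a correlate of protection. Because no visit is named, the visit could also be chosen after results are seen.

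**Working it through.** **Plan's own figures.** Neither document gives a sample size or power for immunogenicity. The primary-endpoint figures reproduce (212 per arm with continuity correction; 86.6% power at 250 per arm, against 86% stated), and nothing here changes them.

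**1. Value of the V2 covariate.** With correlation r between V2 and a later value, adjustment multiplies the variance of the treatment contrast at that visit by 1 − r². It is therefore worth 1/(1 − r²) times the sample. The documents do not give r.

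| assumed r | 1 − r² | worth × sample |
|---|---|---|
| 0.1 | 0.99 | 1.01 |
| 0.3 | 0.91 | 1.10 |
| 0.5 | 0.75 | 1.33 |
| 0.7 | 0.51 | 1.96 |

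**2a. Late samples, closed form.** Assume that the response has no true effect, that every viremic subject is sampled after viremia, and that viremia shifts the log10 response by s. With response SD σ, the odds ratio (OR) per log10 for staying viremia-free is exp(−s/σ²).

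| s | σ = 0.5 | σ = 1.0 | σ = 1.5 |
|---|---|---|---|
| +0.5 | 0.14 | 0.61 | 0.80 |
| −0.5 | 7.4 | 1.65 | 1.25 |
| +0.1 | 0.67 | 0.90 | 0.96 |

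When fewer subjects are sampled late, the distortion shrinks. At +0.5 and σ = 1.0, the OR is 0.78 with half late and 0.89 with a quarter late. At +0.1 with a quarter late, p < 0.05 occurs in 5–6% of runs, so there is no material distortion.

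**2b. By visit, simulated.** All inputs are assumed:
- 500 subjects, 50% viremic by one year (the phase 2 rates in Protocol 1.3.2.2 were 33% and 62%, with a different assay and threshold);
- lognormal viremia times with median 30, 45 or 60 days and log-scale SD 0.6;
- 25% mortality, 85% of living subjects sampled, σ = 1.0, and a shift of +0.5 starting at viremia.

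With no true effect:

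| median (days) | V5 late | V5 OR (p < 0.05) | V8 late | V8 OR (p < 0.05) |
|---|---|---|---|---|
| 30 | 42% | 0.82 (53%) | 93% | 0.64 (100%) |
| 45 | 21% | 0.90 (18%) | 79% | 0.68 (96%) |
| 60 | 11% | 0.94 (9%) | 63% | 0.73 (87%) |

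Here late means the share of viremic subjects sampled after viremia. A landmark Cox analysis of subjects still viremia-free at the sample gave hazard ratios (HR) of 0.98–1.01, with p < 0.05 in 3–6% of runs. The V5 columns spread V5 evenly over day 14 to 40 and so overstate lateness. If all V5 samples were taken on day 14, the late share would be Φ(ln(14/median)/0.6) = 10%, 3% and 1%.

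**2c. With a real protective effect.** The true HR is 0.7 per log10 of a latent level whose SD is 0.85 of the total, so the expected observed HR is 0.7^(0.85²) = 0.77. Without a shift the unrestricted OR is about 1.43. At V8 with medians of 30 and 45 days, a shift of +0.5 gives 0.88 and 0.94 (reversed), and −0.5 gives 2.27 and 2.13 (inflated). The landmark HR stays at 0.77–0.80.

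**2d. What the landmark cannot remove.** If the response starts to shift before viral load reaches 1000 IU/mL, some bias remains. At V5, with no true effect and a +0.5 shift, an assumed 7-day lead gives HR 1.13, 1.07 and 1.04 at the three medians (p < 0.05 in 28%, 16%, 8%). A 14-day lead gives 1.23, 1.15 and 1.10 (58%, 40%, 22%).

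**The case against.** **Baseline adjustment is a choice.** Leaving baseline out of a randomized comparison is valid. The protocol's own comparison is a Wilcoxon test at each visit, and the repeated measures model is an addition in the SAP. At r = 0.1 the gain is 1%, and r may be low for T cells after conditioning and a donor graft. This stands, so the first part is a gain in precision and not the repair of an error.

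**Silence is not a commitment.** The SAP does not say that post-viremia samples will be used, and the size and sign of any shift are assumed. That also stands, and it limits what can be said about size. It does not answer the point: most of the scheduled samples come after the expected time of first viremia, and nothing in the section keeps them out.

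**A landmark has limits.** AVT may be started on local or central results and clinical condition, with no stated threshold (Protocol 2.2.1), so a rule based on central viral load alone would keep treated subjects in. Few events also remain at V9 and V11. Both points stand and shape the fix.

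**Readings that go too far.**
- A reader might infer that omitting V2 biases the treatment comparison through samples missing selectively in one arm. The documents tie missing samples to lymphocyte count and skipped doses, not to arm or to V2 level.
- A reader might also infer that the V8 sample is always lost when dose 3 is skipped for low platelets. Protocol 5.1.1 omits the dose follow-up visit, but footnote 14 of Table 1 omits only the follow-up safety laboratory and reactogenicity assessment. The two passages must be reconciled.

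**Conclusion.** Both gaps are real and both are confined to exploratory analyses.

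Omitting V2 loses precision. The gain from adding it runs from 1% to nearly double the sample over r = 0.1 to 0.7, and r is unknown.

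The correlate analysis as written lets samples taken after viremia act as predictors, and V14 lies at the end of the outcome window. With an assumed shift of half a log10 and SD 1.0, V8 would show a false association in 87–100% of runs and could reverse a real effect. With a shift of 0.1 and a quarter of viremic subjects sampled late, nothing material happens. The documents do not say which case applies, so the finding is a design weakness and not a demonstrated bias. V5 is much less exposed than V8 if it is drawn near day 14 as intended.

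The documents do not support any inference that primary or key secondary conclusions are affected, because none of those analyses uses the immune measurements.

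**What to change.** Amend SAP 7.4.3.3 before unblinding.

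1. Add log10 V2 and V2-by-time as covariates, or use a constrained-baseline model, which keeps subjects without a V2 T-cell sample.
2. Make V5 the main landmark and V8 supportive. At each, include subjects who are alive, have had no central-laboratory viral load ≥ 1000 IU/mL and have not started CMV-specific AVT by the sample date. Predict later viremia through one year, with death before viremia as a competing event.
3. Derive any ROC cutoff from these landmark sets only, and report the number of later viremias at each. Use V9 and V11 for description only, and do not use V14 as a predictor.
4. State that replication below 1000 IU/mL at the sample can still influence the result. Add a sensitivity analysis that excludes subjects with any detectable central viral load at the sample.
5. Reconcile Protocol 5.1.1 with footnote 14 on what is omitted after a skipped dose, so that the expected number of V8 samples is clear.

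Items 1 to 4 cost SAP wording and programming on data already collected. The price is fewer subjects and events. In the simulation (medians 30, 45, 60 days), later viremias numbered about 14, 42 and 74 at V8, 7, 24 and 48 at V9, and 0, 2 and 6 at V11. Power for the real effect was 79–93% at V5 and 14–56% at V8. The AVT exclusion was not simulated and would lower these counts further.

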3.3 Randomization

At the Screening Visit, after the Informed Consent Form (ICF) has been signed, the subject receives a subject number assignment through the IRT for use throughout the study.

Subjects who subsequently meet all inclusion and none of the exclusion criteria will be randomly assigned to receive either ASP0113 or placebo. The randomization to treatment groups will be equally allocated in a 1:1 ratio and stratified by donor-recipient relatedness and donor CMV serostatus.

The IRT vendor generates the randomization schedule. To obtain the randomized treatment assignment for a subject, the pharmacist or designee utilizes an IRT, which is available 7 days a week, 24 hours a day.

Randomization is done after the completion of the Screening period, and at least 14 to 3 days prior to the anticipated transplant day (Day 0). After submitting required information about the eligible subject, the drug kit number assignment is provided. Study drug assignment remains blinded to all site staff except the pharmacist and designated staff.

Randomization of subjects will continue until approximately 500 subjects have been received at least 1 dose of the study. Subjects who discontinue the study early after receiving the first dose of study drug will not be replaced.

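### The ROC-area rule for choosing gB and pp65 cut-offs selects nothing as literally written; on its workable reading it is uncorrected and unadjusted, so a null marker can look weakly predictive

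*SAP*

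**What the plan says.** SAP 7.4.3.3 plans, as an exploratory analysis, that "the relationship between immunogenicity variables and treatment outcome will be assessed using logistic regression method". The outcome is binary: "The treatment outcome is if subject is free of CMV viremia through one year post-transplant". Cut-offs come next: "The optimal cutoff values of the respective immunogenicity variables that will define the treatment outcome will be explored in terms of maximizing the area"; the area meant is that of the ROC curves. The analysis set is fixed: "All analyses of immunogenicity variables will be based on the IAS".

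For this step the section names no covariates, visit, hold-out sample, cross-validation or bootstrap, and no correction for the cut-off search. The repeated-measures model in the same section is specified more fully, as one "where the randomization stratum, treatment, time, and treatment by time interaction will be the explanatory variables". SAP 6.1.4 lists two markers, sampled "On Visits V2, V5, V8, V9 and V11 and V14", and expects a rise in gB-specific antibody "levels and the T-cell response to the pp65 protein over time compared with the placebo group". Randomisation is "stratified by donor-recipient relatedness and donor CMV serostatus" (SAP 3.3).

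**The concern.** There are three gaps.

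- **The criterion.** The ROC area of a continuous marker summarises all cut-offs at once, so it cannot rank them. A programmer must guess what was meant.
- **The search.** If the marker is dichotomised and the two-point area maximised, the same subjects choose the cut-off and supply its reported performance. The maximum over many candidates is biased upwards, and nothing in the section corrects for this.
- **The model.** Vaccine is expected to raise both markers and to lower viremia. A model without arm can therefore link marker and viremia when no link exists within either arm. Donor serostatus could act in the same way.

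At stake is how far a reported gB or pp65 threshold, with its sensitivity, specificity and odds ratio, can be trusted. The trial's efficacy conclusion is not at stake.

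**Working it through.** **The plan's own figure.** SAP 7.4.3.3 gives no number for this analysis. The SAP's one calculated figure is the sample size in section 4, which supplies the upper limit on N used here. With p₁ = 0.353, p₂ = 0.225, d = 0.128 and mean 0.289:

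n′ = [1.96·√(2·0.289·0.711) + 0.842·√(0.353·0.647 + 0.225·0.775)]² / 0.128² = 195.7

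Continuity correction: n = (n′/4)·[1 + √(1 + 4/(n′d))]² = 211.03, so 212 per arm, as stated. Power at 250 per arm is 86.6% by a continuity-corrected normal approximation; the SAP states 86%.

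**Inputs for the check**

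- N: 500, 300 or 200. The size of the IAS is not stated; about 500 is the most it can be.
- Viremia: 33% on ASP0113 and 62% on placebo (protocol 1.3.2.2, phase 2 central laboratory, at 500 copies/mL, used as a proxy for 1000 IU/mL). Viremia-free is then 67% and 38%.
- Markers: normally distributed (assumed). Shifts by arm or donor are assumed.
- Donor-seronegative share: 30%. Protocol 2.2.1 requires at least 30%.

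**Step 1: what the rule means.** A dichotomised marker has a ROC curve with one interior point, so area = (sensitivity + specificity)/2 = (1 + J)/2, where J = sensitivity + specificity − 1 is Youden's index. Maximising one maximises the other.

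**Step 2: the search, with a useless marker.** Every observed value was tried as a cut-off, with and without excluding the outer 10%, in 4,000 trials per setting.

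| N | Continuous area, mean | Best two-point area, mean (either direction) | p < 0.05 at chosen cut, either direction | p < 0.05, direction fixed |
|---|---|---|---|---|
| 500 | 0.500 | 0.538 | 41–43% | 22–26% |
| 300 | 0.50 | 0.549 | 41–42% | 21–24% |
| 200 | 0.50 | 0.559 | 40–41% | 21–24% |

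An area of 0.538 corresponds to J = 2 × 0.538 − 1 = 0.076. Without any cut-off search, the rank test on the continuous marker gives p < 0.05 in 4.8% (N = 500). In a 250/250 split, the area averages 0.553 in the half that chose the cut-off and 0.500 in the held-out half, so the excess comes entirely from the search.

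**Step 3: several looks.** Two markers at six visits make 12 pairs. Treated as independent null looks, the best area averages 0.56 and at least one nominal p < 0.05 occurs in 99.8% of trials. Real looks are correlated, so this is an upper bound.

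**Step 4: arm left out.** Take a continuous marker shifted by δ SD on vaccine, with no relation to viremia within arm. The vaccine share is 0.67/(0.67 + 0.38) = 0.638 among viremia-free subjects and 0.33/(0.33 + 0.62) = 0.347 among viremic subjects, a difference of 0.291. Then

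Pooled area = 0.5 + 0.291·[Φ(δ/√2) − 0.5]

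The null standard error is √[501/(12·262.5·237.5)] = 0.0259.

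| δ (assumed) | Area, formula | Area, simulated | p < 0.05, formula | p < 0.05, simulated | p < 0.05, stratified |
|---|---|---|---|---|---|
| 0.25 | 0.520 | 0.519 | 12% | 12% | 5% |
| 0.5 | 0.540 | 0.540 | 34% | 33% | 4% |
| 1.0 | 0.576 | 0.576 | 83% | 84% | 5% |

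A donor-serostatus shift of 0.5 SD with donor odds ratio 2 (both assumed) and no arm effect gives an area of 0.521 and 12%. Arm and donor shifts of 0.5 SD together give 0.555 and 57%, or 87% once the cut-off is also searched. With no vaccine or donor effect on viremia, omitting arm does nothing (area 0.500, 5%).

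**Step 5: timing.** Protocol 2.2.2 expects first viremic episodes at about day 30. V5 falls on days 14–40, V8 is 10–14 days after the day-60 dose, V9 is about day 90, V11 about day 180 and V14 day 365 or later. Many samples from V8 onwards would follow the event they are meant to predict.

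**The case against.** The strongest reply is that a sensible statistician would dichotomise, which makes the rule Youden's index under another name; the plural ROC curves may even mean one curve per candidate cut-off. That stands: a workable reading exists, and the optimism in Step 2 arises only on that reading. The literal reading gives no optimism, but no cut-off either.

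Other parts of the reply also stand:

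- A reader might infer that the SAP pools arms and donor groups. It does not say so. The section is silent, although neighbouring models (SAP 7.4.2.1, 7.4.3.1.2 and the repeated-measures model) do name treatment and stratum.
- A reader might infer that a useless marker will look predictive. For one marker and visit the area is near 0.54, at N = 500 no simulated trial reached 0.60, and the p-value at the chosen cut is one the SAP does not plan.
- Near-certainty of a false lead requires picking the best of many marker-visit pairs, which the SAP does not propose.
- Nothing in the documents says that a cut-off would guide later doses or populations.
- Arm is not a plain confounder. The vaccine is meant to act through these responses, so models with and without arm answer different questions.

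The exploratory label limits the consequence. It does not supply a cut-off criterion or remove the bias in the reported figures.

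**Conclusion.** The concern holds in limited form. Read literally, the rule cannot choose a cut-off. Read workably, it inflates a null marker's area from 0.50 to about 0.54–0.55 at N = 300–500, with nominal significance at the chosen cut in about 40% of trials (21–26% with direction fixed), and more if several visits are searched. Leaving out arm adds a further false association only if the vaccine moves both marker and viremia: about 12% to 33% for an assumed 0.25–0.5 SD shift, against about 5% stratified. The search figures rest on an assumed IAS size and on phase 2 viremia rates as a proxy; the arm and donor figures also rest on normal markers and on shift sizes and a donor odds ratio that the documents do not give. The matter is worth correcting because following the stated rule gives biased performance figures, but it stays within an exploratory analysis and does not touch the primary or key secondary tests.

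**What to change.** In SAP 7.4.3.3:

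1. Report the ROC area of each continuous marker once, with no cut-off attached.
2. Name Youden's index as the cut-off criterion.
3. Repeat the whole search, including any choice of marker and visit, in bootstrap resamples, and report optimism-corrected sensitivity, specificity and area.
4. Fit the logistic model with treatment arm, donor CMV serostatus and donor-recipient relatedness, and show the model without arm alongside.
5. Use only samples taken before a subject's first viremia. Bootstrap and covariates cannot repair a predictor measured after the event.

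The cost is SAP wording and a resampling loop, with no new data. The corrected figures will look less favourable, and step 5 leaves fewer subjects at later visits.
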